**4. Objectives, Endpoints and Hypotheses**

**4.1 Objectives and Endpoints**

Objectives	Endpoints
Phase 1b	
Primary	

 
Establish the safety and tolerability of AMG 420 at dose levels of 400 µg/day and 600 µg/day in subjects with relapsed and/or refractory multiple myeloma (RRMM)
 
	
 
Dose-limiting toxicities (DLTs), treatment-emergent adverse events, treatment-related adverse events, and changes in vital signs, electrocardiograms (ECGs), and clinical laboratory tests
 

Key Secondary	

 
Estimate overall response rate (ORR) and duration of response (DOR) of AMG 420 in subjects with RRMM
 
	
 
ORR
 
DOR
 

 
Evaluate the rate of minimal residual disease (MRD)-negativity at the time of CR
 
	
 
MRD negativity at the time of CR
 

Secondary	

 
Establish the safety and tolerability of AMG 420 in subjects with extramedullary relapsed multiple myeloma
 
	
 
DLTs, treatment-emergent adverse events, treatment-related adverse events, and changes in vital signs, ECGs, and clinical laboratory tests
 

 
Characterize the pharmacokinetics (PK) of AMG 420 when administered as 4-week continuous intravenous (cIV) infusion
 
	
 
AMG 420 PK parameters including, but not limited to, half-life (<math>t_{1/2}</math>), clearance, and apparent <math>C_{ss}</math>
 

Objectives	Endpoints
Secondary	

• Evaluate other measures of anti-myeloma activity of AMG 420 in subjects with RRMM:

– Time to response

– Progression-free survival (PFS)

– Overall survival (OS)

– Best overall response (BOR)

	

• Efficacy parameters according to International Myeloma Working Group (IMWG) response criteria, per investigator assessment:

– Time to response

– PFS

– OS

– BOR

Objectives	Endpoints
Exploratory	

---

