#### **9.2.3.3 Electrocardiograms (ECGs)**

Subject must be in supine position in a rested and calm state for at least 5 minutes before ECG assessment is conducted. If the subject is unable to be in the supine position, the subject should be in most recumbent position as possible. ECGs should be performed in a standardized method, in triplicate, and run consecutively (ie, approximately 60 seconds apart), prior to blood draws or other invasive procedures. Each ECG must include the following measurements: QRS, QT, QTc, RR, and PR intervals.

- $\geq 3$  baseline ECGs collected  $\geq 30$  minutes apart, with each baseline ECG in triplicate run consecutively (ie, approximately 60 seconds apart) [ie, total  $\geq 9$  ECGs]
- Single ECGs at time points after dosing

The Baseline ECG QTc (defined as the average of the individual baseline ECGs), should not be  $> 470$  msec (applying Fridericia correction). Baseline is defined as predose assessments from cycle 1 day 1. The investigator or designated site physician will review all ECGs. ECGs will be transferred electronically to an ECG central reader for analysis per Amgen instructions. Once signed, the original ECG tracing will be retained with the subject's source documents. At the request of the sponsor, a copy of the original ECG will be made available to Amgen. Standard ECG machines should be used for all study-related ECG requirements.

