	
protocol-required therapies, and significant treatment-emergent adverse events will also be provided.
 
Dose Limiting Toxicities
 
The analysis of the probability of DLTs will include data from DLT-evaluable subjects (see Section 7.4.1 for definition of DLT-evaluable). The primary analysis will only include DLTs that occur within the first cycle. If DLTs occur outside the first cycle, a sensitivity analysis will be performed where DLTs occurring outside of the specified time interval are included. The number and percentage of subjects reporting DLTs will be evaluated overall and by AMG 420 dose level and part.
 
Clinical Laboratory Tests
 
Clinical chemistry, hematology, and urinalysis data will be listed and reviewed for each subject. Values outside the normal laboratory reference ranges will be flagged as high or low on the listings. Depending on the size and scope of changes in laboratory data, the analyses of safety laboratory endpoints will include summary statistics over time and/or changes from baseline over time. Maximum shifts in grades of selected safety laboratory values between baseline and the worst on-study value may be tabulated.
 
Vital Signs
 
Vital signs data will be listed and reviewed for each subject. Depending on the size and scope of changes, the analyses of vital signs may include summary statistics over time and/or changes from baseline over time.
 
Electrocardiograms
 
Summaries over time and/or changes from baseline over time will be provided for all ECG parameters. Subjects' maximum change from baseline in QTcF will be categorized and the number and percentage of subjects in each group will be summarized. Subjects' maximum post baseline values will also be categorized and the number and percentage of subjects in each group will be summarized. All on-study ECG data will be listed, and select parameters of interest may be plotted.

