* If death or PD is more than 84 days after previous disease assessment, or Study Day 1 if there is no previous disease assessment.

** Only apply to PFS.

Overall survival (OS)

Overall survival is defined as the interval from Study Day 1 until death due to any cause; otherwise, OS is censored on the last recorded date on which the subject was alive.

Last Evaluable Disease Assessment Date

For responses assessed by investigator, last disease assessment date is the last evaluable response assessment date collected using IMWG Response CRF (except the response assessment date of Inevaluable) before confirmed PD, on or before new anti-cancer therapies or procedures.

Last Known Alive Date

For subjects not known to have died, their last date known to be alive will be determined as the latest date associated with clinic visits before data cutoff date including, for example, but not limited to the following:

- Date of Enrollment on Subject Enrollment CRF
- Date First Taken, Date Last Taken on Concomitant Medications CRF

- Date Performed on ECOG Performance Status, Vital Signs, Electrocardiogram, Procedures CRFs
- Admission Date, Discharge Date on Hospitalizations CRF
- Date of Examination on Physical Measurement CRF
- Date Collected on Reproductive Status and Pregnancy Test (Local Lab), Chemistry (Local Lab), Hematology (Local Lab), Coagulation (Local Lab), Urinalysis (local Lab), Immunology (Local lab) CRFs and in central lab data
- Date of Assessment on IMWG Response for Time Point, Peripheral Neuropathy Assessment CRFs
- Start Date and End Date on Investigational Product Administration CRF
- Date Started and Date Ended or Resulted in Death on Events CRF
- Start date, Stop date on Anti-Myeloma / Anti-Cancer Therapies, Other Protocol Required Therapy (GLUCOCORTICOID), Other Protocol Required Therapy (Tocilizumad), Hematopoietic Stem Cell Transplantation Autologous, Hematopoietic Stem Cell Transplantation Allogenic CRFs
- Subject Status Date if status is Alive on Survival Status CRF
- Assessment Date on Skeletal Survey and Plasmacytoma Assessment CRF
- **End_of study date if the subject's primary reason for ending study is not "Lost to follow-up"**

Fridericia-corrected QT Interval (QTcF)

The Fridericia correction will be calculated from the investigator reported QT (msec) and RR interval (msec), as follows:

$$QTcF = QT / (RR/1000)^{1/3}$$

Change From Baseline

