9.6.6 Electrocardiogram

Summaries over time and/or changes from baseline over time will be provided for all ECG parameters. Subjects' maximum post baseline values will be categorized and the number and percentage of subjects in each group will be summarized.

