9.7.5 Analyses of Biomarker Endpoints

The analysis of Biomarker will be described and performed by Clinical Biomarker Group.

10. Changes From Protocol-specified Analyses

There are no changes to the protocol-specified analyses.

11. Literature Citations / References

12. Prioritization of Analyses

No Priority of outputs planned for this study

13. Data Not Covered by This Plan

The analysis of Biomarkers (except MRD) is not covered in this plan.

14. Appendices

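### SAP Section 5 derives QTcF from investigator-reported intervals, although the protocol sends ECGs to a central reader for analysis and the SAP declares no change

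*SAP*

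**What the plan says.** - **Site role.** Protocol Section 9.2.3.3: "The investigator or designated site physician will review all ECGs". The same section lists the intervals that every tracing carries: "Each ECG must include the following measurements: QRS, QT, QTc, RR, and PR intervals".
- **Central role.** Protocol Section 9.2.3.3 continues: "ECGs will be transferred electronically to an ECG central reader for analysis per Amgen instructions". It names no visit or subset.
- **Endpoint.** Protocol Section 4.1 includes ECG change in the primary safety endpoint: "treatment-related adverse events, and changes in vital signs, electrocardiograms (ECGs), and clinical laboratory tests". Protocol Section 10.4.2.3.1 plans one QTcF output by name: "Subjects' maximum change from baseline in QTcF will be categorized and the number and percentage of subjects in each group will be summarized".
- **SAP derivation.** SAP Section 5, under the QTcF definition: "The Fridericia correction will be calculated from the investigator reported QT (msec) and RR interval (msec".
- **SAP summaries.** SAP Section 9.6.6 summarises all ECG parameters over time without naming a data source, and adds: "Subjects' maximum post baseline values will be categorized and the number and percentage of subjects in each group will be summarized".
- **SAP on departures.** SAP Section 10: "There are no changes to the protocol-specified analyses".

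**The concern.** The protocol arranges a uniform read of the tracings by one reader. The SAP then writes a derivation rule that picks the other read, the one reported by each site. A programmer following SAP Section 5 would build QTcF from site values and would have no instruction to bring in the central ones. Because Section 10 lists no departures, nothing tells a reader of the results that a choice was made.

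At stake is the quality of one component of the primary safety endpoint. About 20 subjects are planned over about 15 sites, or roughly 20/15 = 1.3 subjects per site, on standard ECG machines. With so few subjects per site, a site's reading habit cannot be told apart from a real difference between subjects.

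**Working it through.** **1. The two rules side by side.** No document figure depends on this point, so there is none to reproduce. The protocol gives ECGs two readers: the site, which reviews, and the central reader, which analyses. The SAP uses QT and RR as the investigator reported them. It never mentions a central ECG read; its only reference to central data is central laboratory data, listed for the last-known-alive date. The same list names an Electrocardiogram CRF.

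**2. Does the version gap explain it?** The SAP is written to protocol amendment 4 and the protocol at hand is amendment 5. The amendment 5 rationale does not list Section 9.2.3.3 among the sections changed, so the gap offers no explanation.

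**3. How a read difference reaches QTcF.** The SAP formula is QTcF = QT / (RR/1000)^(1/3), with both intervals in ms. A QT difference d therefore shifts QTcF by d / (RR/1000)^(1/3). The divisor is 1 at RR 1000, 0.909 at RR 750 and 0.843 at RR 600. The inputs below are assumptions (QT 400 ms, differences of 5 to 20 ms), because the documents give no size for read differences.

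| RR (ms) | QTcF at QT 400 | QT +5 | QT +10 | QT +20 | RR +20 |
|---|---|---|---|---|---|
| 1000 | 400.0 | +5.0 | +10.0 | +20.0 | -2.6 |
| 750 | 440.3 | +5.5 | +11.0 | +22.0 | -3.8 |
| 600 | 474.3 | +5.9 | +11.9 | +23.7 | -5.2 |

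A QT read difference passes through one-for-one at RR 1000 and is slightly enlarged at shorter RR.

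**4. Which outputs carry it.** Write a site reading as the true value plus a constant site offset b plus random error.
- Maximum post-baseline value (the categorised output in SAP Section 9.6.6): b stays in full.
- Change from baseline: b largely cancels if the same site reads both, since (true post + b) - (true baseline + b) = true post - true baseline.
- Averaging repeat tracings, as SAP Section 5 does, shrinks random error (by 1/√3 = 0.58 for three independent reads) but leaves b untouched.

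The categorised output that SAP Section 9.6.6 plans is thus the one in which a site offset survives. The categorised maximum change of Protocol Section 10.4.2.3.1 does not appear there.

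**5. What cannot be computed.** The documents give no reading variance, no site-to-site spread and no category limits for the ECG outputs. The number of subjects who would change category is therefore not derivable.

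**The case against.** **The protocol does not call the central reads the analysis dataset.** This stands. It says the tracings go to the central reader for analysis under sponsor instructions, which are not in the documents. Its statistical section names no ECG source. A reader might infer that Section 10 of the SAP is plainly false; the documents do not go that far. They do show that the SAP states a rule for QTcF which passes over a read the protocol requires, without comment.

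**The SAP rule covers QTcF only.** Also correct. A reader might infer that central reads are unused for every ECG parameter. For the others the SAP is silent, and non-use is only an inference from that silence.

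**Averaging and a common formula already limit the noise.** In part. One Fridericia formula at all sites removes differences in correction method, and averaging reduces random error. How much averaging takes place after dosing is unclear: Protocol Section 9.2.3.3 asks for single post-dose ECGs, while the schedules list triplicates. Neither step removes a site offset from an absolute maximum.

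**A reader might want a count of spurious outliers.** One can assume a 30 ms limit on maximum change, 8 independent post-baseline time points and no drug effect, and compute 1 - Φ(30/SD)^8. An SD of 15 ms gives 16.8%. Averaging three independent reads gives 15/√3 = 8.7 ms and about 0.2%. The answer is set by the assumed SD. Both readers see the same tracings, so biological variation is common to both. The output is also one that SAP Section 9.6.6 does not plan. The documents support no such count.

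**A reader might infer that central reading cures open-label bias.** Sites do know dose and timing, but nothing says the central reader is blinded to either. No such benefit is claimed.

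**The endpoint is descriptive.** True: ECG change is one item in a list, QTcF drives no hypothesis or decision rule in the analysis, and enrolment holds rest on dose-limiting toxicities. This limits the consequence but does not justify the less standardised input.

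**Conclusion.** The mismatch is real. For QTcF, the SAP selects investigator-reported intervals where the protocol provides for a central read, and neither declares nor justifies the choice. The effect is avoidable between-site reading variation in one component of a descriptive primary safety endpoint. It reaches QTcF about one-for-one and stays in the categorised maximum post-baseline values.

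Its overall size is unknown. The conclusion rests on two readings of the text: that the protocol's unrestricted sentence covers the study ECGs generally, and that central analysis was meant to produce usable interval values. If the sponsor's instructions give the central read a narrower purpose, what remains is an undeclared data-source choice that the SAP should explain. The point is worth correcting because the correction is simple, not because results are shown to be wrong.

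**What to change.** - **SAP Section 5:** compute QTcF from the central reader's QT and RR, at baseline and at every post-baseline assessment, so that both sides of a change come from the same source.
- **SAP Section 9.6.6:** state that all ECG summaries use central reads.
- **Investigator values:** present them in a listing. Use them in the summaries only where a central read is missing, with a flag.
- **If central reads are not available as an analysis dataset under the sponsor's instructions:** say so in SAP Section 10 and justify the investigator-read source there.

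The cost is a few lines of SAP text and a change of input dataset. The protocol already requires the transfer of tracings to the central reader. The SAP, however, names only the RAVE database and describes no central ECG data transfer, so the central data must be brought in and integrated. Site review of ECGs during the study is unaffected.

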6.1 Safety Analysis Set

Safety Analysis Set defined as all subjects that are enrolled and receive at least 1 dose of AMG 420.

6.2 Dose Limiting Toxicity Evaluable Analysis Set

The analysis of DLT will be restricted to DLT-evaluable subjects. **DLT evaluable analysis set includes subjects who complete the DLT evaluable period or experienced a DLT anytime during the DLT evaluable period.** A subject will be not DLT evaluable if he/she drops out before completion of the DLT-evaluable period for reasons other than a DLT prior to completing the 4 weeks of AMG420 treatment.

The DLT window may also be extended to assess events starting within the window in case the DLT definition is time dependent.

6.3 Pharmacokinetic/Pharmacodynamic Analyses Set(s)

The PK Analysis Set will contain all subjects who have received at least 1 dose of the investigational product and have at least 1 PK sample collected. These subjects will be evaluated for PK analysis unless the number of data points required for analysis is not enough, or significant protocol deviations have affected the data, or if key dosing or sampling information is missing.

6.4 Retreatment Analysis Set

Retreatment analysis set defined as subjects that are enrolled and receive at least one dose of AMG 420 during the second course of treatment after attaining CR and subsequently have disease progression while off-therapy.

7. Planned Analyses

7.1 Interim Analysis and Early Stopping Guidelines

7.1.1 Interim Analyses

No specific interim analysis planned.

7.1.2 Dose Level Review Team

DLRT will be responsible for monitoring safety and making recommendations regarding termination of enrollment and dose level/schedule escalation/changes. See Protocol Section 12.3 for further details of DLRT responsibilities.

7.2 Primary Analysis

The primary analysis will occur when the target enrollment is complete and each subject has had the chance to be treated for at least 6 months.

7.3 Final Analysis

A final analysis is planned after all subjects have ended the study.

8. Data Screening and Acceptance

8.1 General Principles

The objective of the data screening is to assess the quantity, quality and statistical characteristics of the data relative to the requirements of the planned analyses. The database will be subject to edit checks outlined in the data management plan (DMP) by Amgen Clinical Data Management (CDM) department. Data inconsistencies and suspicious values will be reviewed and resolved before the database is locked.

8.2 Data Handling and Electronic Transfer of Data

The Amgen Global Study Operations-Data Management (GSO-DM) department will provide all data to be used in the planned analyses. This study will use the RAVE database.

8.3 Handling of Missing and Incomplete Data

The following imputation for missing or incomplete data will be performed if required:

Incomplete adverse event and concomitant medication dates missing data will be imputed as described in [Appendix A](#).

Non-pharmacokinetic measurements (eg, biomarker data) that are below the lower limit of quantification will be considered equal to half of the lower limit of quantification for all analyses unless specified otherwise.

8.4 Detection of Bias

Lack of protocol compliance and the potential for biased statistical analyses will be examined by assessing the incidence of important protocol deviations in each cohort. The clinical study team will identify and document the criteria for important protocol deviations.

8.5 Outliers

Outlier data will not be excluded unless scientifically justified.

Pharmacokinetic (PK) serum concentration data will be evaluated for outliers by visual inspection, and decisions to re-assay individual samples will be made in accordance with standard pharmacokinetic evaluation practice.

8.6 Distributional Characteristics

Where appropriate, the assumptions underlying the proposed statistical methodologies will be assessed. If required data transformations or alternative non-parametric methods of analyses will be utilized.

8.7 Validation of Statistical Analyses

Programs will be developed and maintained, and output will be verified in accordance with current risk-based quality control procedures.

Tables, figures, and listings will be produced with validated standard macro programs where standard macros can produce the specified outputs.

The production environment for statistical analyses consists of Amgen-supported versions of statistical analysis software; for example, the SAS System version 9.4 or later.

9. Statistical Methods of Analysis

9.1 General Considerations

Descriptive statistics will be provided for selected demographics, safety, PK, pharmacodynamic and biomarker data by dose, dose schedule, and time as appropriate. Descriptive statistics on continuous data will include means, medians, standard deviations and ranges, while categorical data will be summarized using frequency counts and percentages. Time to event endpoints will be summarized with Kaplan-Meier (KM) proportions at select time points, KM quartiles (when estimable), the number of

subjects with events, the number of subjects censored, and censoring reasons. Duration of follow-up for time to event endpoints will be estimated using the reverse Kaplan Meier method (Schemper and Smith, 1996). Point estimates for efficacy endpoints will be accompanied by 2-sided 95% confidence intervals including KM quartiles (Klein and Moeschberger, 1997), KM proportions (Kalbfleisch and Prentice, 1980), and binomial proportions (Clopper and Pearson, 1934). Graphical summaries of the data may also be presented.

9.2 Subject Accountability

The following subject disposition information will be summarized as follows

- Number of screened subjects
- Number of subjects in Safety Analysis Set
- Number (%) of subjects who discontinued treatment
- Number (%) of subjects who discontinued the study
- Primary reason for ending treatment
- Primary reason for study discontinuation

The percentages are based on the number of subjects **enrolled in the study**.

9.3 Important Protocol Deviations

Important Protocol Deviations (IPDs) categories are defined by the study team before the first subject's initial visit and updated during the IPD reviews throughout the study prior to database lock. These definitions of IPD categories, subcategory codes, and descriptions will be used during the course of the study. Eligibility deviations are defined in the protocol.

9.4 Demographic and Baseline Characteristics

The following descriptive summaries of the demographic and baseline characteristics will be produced: Demographic (ie, age, age groups [< 65 , 65-74 and ≥ 75], sex, race, ethnicity), prior line of therapies (median, range) and baseline characteristics (height, weight, Eastern Cooperative Oncology Group (ECOG) Performance Status will be summarized using descriptive statistics. If multiple races have been reported for a subject, the subject will be categorized as multiple.

9.5 Efficacy Analyses

9.5.1 Analyses of Key Secondary Efficacy Endpoint(s)

9.5.1.1 Overall Response Rate

The number (%) of subjects with a best overall response of sCR, CR, VGPR, PR, MR, SD, PD or IE will be summarized.

Overall response rate is defined as the proportion of subjects for whom the best overall response is sCR, CR, VGPR, or PR as determined by International Myeloma Working Group Uniform Response Criteria (IMWG-URC). The ORR along with the associated 95% exact binomial confidence interval (Clopper-Pearson method) will be determined.

